## 7 SUBJECT CONFIDENTIALITY

Participant confidentiality will be maintained during and after the interview in several ways:

- The interview will be conducted in a private place where the interview cannot be overheard.
- Interviewers will be trained in research integrity and ethics, including protecting participant information.
- Informed consent will be conducted verbally, thereby reducing the risk of a breach of client confidentiality by eliminating any paper record of clients' participation in the study with signature.
- Data will be collected on tablets which will be encrypted and password protected.
- Individuals will be assigned a unique study ID. No information that could be used to identify the participant will be recorded such as names, identification numbers, dates of birth or address.
- Anyone older than 80 years of age will be recorded as '80.'
- Data will be transferred from the tablet to a secure, password protected computer once per week.
- Data will be stored on an encrypted, password protected computer and backed up on Duke Box. The data will only be accessible to the Data Manager and the PI. It will be reviewed regularly to ensure quality and completeness.
- Only fully de-identified data will be provided to other study personnel or statisticians. Only fully de-identified data will be shared.

### 7.1 Future Use of Stored Specimens

Not applicable.

## **8 INFORMED CONSENT PROCESS**

Informed consent will be obtained prior to collecting any participant information for research purposes. Clients will be approached as they leave the PPMV and asked if they would be willing to participate in a brief interview. If so, the interviewer will conduct screening and consent in a private area away from other clients. The client will be given time to ask questions and will be asked to give verbal consent for the interview, which will be documented by the interviewer. The interviewer will explain the purpose of the study, the risks, benefits, and safeguards in place to protect the participant's information. A printed copy of the consent script will be available for them to read and to keep. Contact information for the Study Coordinator or PI will be provided so the participant can ask questions after the interview.

No individual identifying information will be collected during the interview, therefore withdrawing consent after the interview is closed will not be possible. To mitigate this, the interviewer will confirm consent by asking at the end of the survey if the participant is comfortable with all the answers and agrees for their information to be retained.

### **8.1 Informed Consent/Assent Process (in Case of a Minor or Others Unable to Consent for Themselves)**

The study will only enroll minor participants present with a parent or guardian and all questions will be directed to the parent/guardian. Therefore, we do not anticipate interacting with minors or needing assent from the minor.

We will not enroll individuals who are unable to consent for themselves such as those who are mentally impaired or are experiencing impaired consciousness.

## SUPPLEMENTS/APPENDICES

### Aim 2: TESTsmART Participant exit interview - Screening Questions

| Number | QUESTION  | RESPONSE   | SKIP                 |
|--------|---|--|----------------------|
| 0.01   | Did the person meet all of the inclusion criteria?   | 1. Yes
2. No  | If yes, skip to 0.03 |
| 0.02   | If no, why were they excluded from participating in the study today? (select all that apply) | 1. Person did not have a fever or malaria-like illness
2. Patient with malaria-like symptoms not present
3. Patient younger than 1 year of age
4. Had symptoms of severe malaria and referred for care
5. Took antimalarial in the last seven days for current illness
6. No parent or guardian present | STOP                 |
| 0.03   | Did the person consent to participate in the study?  | 1. Yes
2. No  | If No, STOP          |

### GENERAL STUDY INFORMATION

| Number | QUESTION                     | RESPONSE   | SKIP |
|--------|------------------------------|--|------|
| 0.1    | Date                  | MM/YYYY  |      |
| 0.2    | Participant ID        |  |      |
| 0.3    | Outlet ID             |  |      |
| 0.4    | Interviewer ID        |  |      |
| 0.5    | Language of interview | 1. English
2. Yoruba
3. Igbo
4. Hausa
5. Other |      |

### SECTION 1: RESPONDENT INFORMATION

| Number | QUESTION   | RESPONSE   | SKIP  |
|--------|--|--|-------|
| 1.1    | Who is the respondent?                    | Adult with fever.....1
Guardian of the child.....2  | →Q1.5 |
| 1.2    | What is your relationship with the child? | Parent.....1
Grandmother/grandfather.....2
Brother/Sister.....3
Uncle/Aunt.....4
Other.....5 |       |

|     |  |                            |  |
|-----|--|----------------------------|--|
|     |  | Specify:                   |  |
| 1.3 | Gender of the child   | Female.....1
Male.....0 |  |
| 1.4 | How old is the child?   | _____. ____ years          |  |
| 1.5 | Gender of the respondent  | Female.....1
Male.....0 |  |
| 1.6 | How old are you?
[In the case the child is ill, please collect this information for the parent/guardian of the child] | _____ years                |  |

## SECTION 2: CURRENT ILLNESS

| Number | QUESTION  | RESPONSE  | SKIP                           |
|--------|---|---|--------------------------------|
| 2.1    | Which symptoms do you/your child have or had in the last 24 hours?
[Mark all that apply]               | 1. Fever
2. Nausea
3. Headache
4. Body aches
5. Vomiting
6. Shivering
7. Stomach ache
8. Other _____
99. Don't know |                                |
| 2.2    | How serious is this illness in your opinion?

[Guardian of the child can guess how the child feels] | 1. Not very serious/minor
2. Moderate
3. Very serious   |                                |
| 2.3    | How many days ago did the symptoms start?  | _____ days  | 99=Don't know                  |
| 2.4    | How likely is it that the illness that you/your child have today is malaria?                                     | 1. Not possible
2. Unlikely but not impossible
3. 50/50
4. Likely
5. Absolutely sure
99. Don't know                          |                                |
| 2.5    | Have you sought treatment or care elsewhere for this illness?  | 1. Yes
2. No
99. Don't know   | If no or don't know, go to 3.1 |

|      |   |   |   |
|------|---|---|---|
| 2.6  | What did you do? Check all that apply  | 
 
1. Buy medicine at general shop
 
2. Visit pharmacy/chemist
 
3. Visit government health center/dispensary
 
4. Visit private clinic
 
5. Visit hospital
 
6. Visit private laboratory
 
7. Gave medicine available at home
 
8. Visit traditional healers
 
9. Visit religious/cultural healers
 
10. Visit community health worker
 
11. Other _____
 
 
99. Don't know (i.e., another caregiver was involved)
 |   |
| 2.7  | Why did you come to this facility?   | 
 
1. Treatment was not available in other facilities
 
2. RDT tests were not available in other facilities
 
3. It's the closest chemist shop to me
 
4. This chemist shop has better prices
 
5. I was referred here for treatment
 
 
99. Don't know (i.e., another caregiver was involved)
  |   |
| 2.8  | Did you have a malaria test from another provider/facility/lab before coming here today? | 
 
1. Microscopy
 
2. RDT
 
3. Don't know
 
4. No test
 
  | If 4, go to 3.1                                 |
| 2.9  | Malaria test results from elsewhere  | 
 
1. Negative – report observed
 
2. Positive – report observed
 
3. Reported negative by respondent
 
4. Report positive by respondent
 
5. Doesn't recall result
 
  |   |
| 2.10 | Do you have a copy of the test result?   | 
 
1. No, nothing written
 
2. Yes
 
  |   |
| 2.11 | Have you taken/given to the child any medication for this illness since it started?      | 
 
1. Yes
 
2. No
 
 
99. Don't know
   | If 1, go to 2.12
If 2 or 99, go to Section 3 |
| 2.12 | If so, which medicines (select all that apply)   | 
 
1. AL (Lonart/CoArtem/Artefan)
 
2. Other ACT (DHAP, DP, Duocotexin, P-alaxin)
 
   | If 1, 2 or 3 STOP                               |

|      |   |   |                         |
|------|---|---|-------------------------|
|      |   | 
3. Monotherapy (Artesunate, Quinine, Chloroquine, SP/Fansidar)
 
4. Antibiotic (Amoxyl/Septrin, Metronidazole/Flagyl, Ampicillin)
 
5. Painkiller/fever medicine (Panadol/Brufen/Hedex/ Action/)
 
6. Cough medicine or decongestant
 
7. Other _____
 
99. Don't know
  |                         |
| 2.13 | Did you come to the chemist/shop today with a prescription from another provider/facility/lab? | 
1. Yes
 
2. No
  | If 2 skip to Section 3. |
| 2.14 | If yes, what was the prescription for?   | 
1. AL (Lonart/CoArtem/Artefan)
 
2. Other ACT (DHAP, DP, Duocotexin, P-alaxin)
 
3. Monotherapy (Artesunate, Quinine, Chloroquine, SP/Fansidar)
 
4. Antibiotic (Amoxyl/Ceprin, Metronidazole/Flagyl/Ampicillin)
 
5. Painkiller/fever medecine (Panadol/Brufen/Hedex/ Action/Maramoja)
 
6. Cough medicine or decongestant
 
7. Other _____
 
99. Don't know
 |                         |

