The primary outcome will be the proportion of all ACTs that are sold to individuals with a positive malaria diagnostic test. The ultimate goal of a conditional subsidy scheme is to limit both inappropriate use of ACTs by those without a test or with a negative test as well as to reduce the programmatic cost of ACT subsidies by offering them conditionally on a positive test at the point of sale. For this outcome, a positive test is anyone who is tested at the outlet and receives a positive result or is referred from a health facility or diagnostic lab with a documented positive test result. Although all ACTs purchased after a test, whether tested at the outlet, health facility or diagnostic lab, are included in the outcome measure, only ACTs purchased following a *test at the outlet* are eligible for the conditional subsidy. Our major secondary outcome is proportion of suspected malaria cases that are tested. This outcome will allow us to determine whether the conditional subsidy can drive demand for testing. Other secondary outcomes will measure 1) adherence to the RDT result among all those tested, 2) proportion of all suspected malaria cases that are managed appropriately (tested for malaria, and use ACT following a positive test and do not purchase an ACT after a negative test), and 3) ACT use by test status (untested, negative, positive).

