## 6 STATISTICAL CONSIDERATIONS

### 6.1 Study Outcome Measures

The primary outcome measure is the proportion of selected ACTs that are sold to individuals with a positive malaria diagnostic test defined as anyone who is tested at the outlet and receives a positive test result or is referred from a health facility or diagnostic lab with a documented positive test result.

$$\frac{\# \text{ people who tested positive and purchased ACT}}{\# \text{ people who purchased ACT}}$$

Among secondary outcomes, behavior will be measured for individuals who were tested at the outlet. Untested clients are those who chose not to be tested and did not come with a test result from another facility. The major secondary outcome is the proportion of suspected malaria cases that are tested. This outcome will allow us to determine whether the conditional subsidy can drive demand for testing. Note that “untested people” here refers specifically to individuals that present at the shop without a referral but decline to be tested.

$$\frac{\# \text{ people who were tested with an RDT}}{\# \text{ people who were tested with an RDT} + \# \text{ untested people who purchased an antimalarial}}$$

Other secondary outcomes will measure 1) adherence to the RDT result among all those tested at the outlet, 2) proportion of all suspected malaria cases that are managed appropriately (tested for malaria, and use ACT following a positive test or do not purchase an ACT after a negative test), and 3) ACT use by untested clients.

- Secondary outcome 2: Adherence to the RDT result among all those tested in the shop

$$\frac{\# \text{ people who tested positive and purchased ACT} + \# \text{ people tested negative and did not purchase any AM}}{\# \text{ people who were tested with an RDT}}$$

For those who are negative, if they buy any antimalarial (AM), including monotherapies and older therapies, they are not adhering to test result.

- Secondary outcome 3: Proportion of all suspected malaria cases that are managed appropriately in the shop

$$\frac{\# \text{ people who tested positive and purchased ACT} + \# \text{ people tested negative and did not purchase any AM}}{\# \text{ people who were tested with an RDT} + \# \text{ untested people who purchased an antimalarial}}$$

“Untested people” here refers specifically to individuals that present at the shop without a referral but decline to be tested

- Secondary outcome 4: ACT use among untested clients

---

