### Section 3: Test at Shop

| Number | QUESTION   | RESPONSE   | SKIP                   |
|--------|--|--|------------------------|
| 3.1    | Did you (or your child) have your blood tested for malaria today at the shop? | 
1. Yes
 
2. No
   | If yes skip to 3.3     |
| 3.2    | Why not? (Mark all that apply)  | 
1. Too expensive
 
2. RDT was not offered
 
3. RDT not in stock
 
4. No time
 
5. Already sure illness is malaria
 
6. Already sure illness is not malaria
 
7. Don't want to get finger pricked
 
8. Was tested elsewhere before coming
 
9. Had a prescription for drug I needed before coming
 
99. Other
 | Next skip to section 4 |

|     |  |  |  |
|-----|--|--|--|
|     |  | Specify: _____                           |  |
| 3.3 | RDT results from shop (self-report) | 1. Negative
2. Positive
3. Invalid |  |
| 3.4 | How much did you pay for the RDT?   | _____ Naira                              |  |

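### The exit form can lose a documented positive test from elsewhere unless the client is retested at the outlet, and because retesting pressure differs by arm this may inflate Arm 4 versus Arm 1

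*Combined protocol and SAP*

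**What the plan says.** **Outcome definition.** The Protocol Summary, Section 3 and Section 6.1 agree. An ACT buyer is in the primary numerator if tested positive at the outlet, or if the client "is referred from a health facility or diagnostic lab with a documented positive test result". Section 6.1 adds that outside positives are kept in the primary outcome on purpose and left out of the secondary outcomes.

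**Exit form, Section 2.** Item 2.5 asks "Have you sought treatment or care elsewhere for this illness". The skip beside it reads "If no or don't know, go to 3.1". Whether there was an outside test ("Did you have a malaria test from another provider/facility/lab before coming here today"), its result and whether the client has a copy are items 2.8, 2.9 and 2.10, all after that skip. Item 2.9 separates results the interviewer saw from those only stated, the latter including "Report positive by respondent" (code 4).

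**Exit form, Section 3.** A client not tested at the outlet is asked why at 3.2. Option 8 is "Was tested elsewhere before coming". Every answer to 3.2 leads to Section 4, and no outside result is recorded. An outlet result is taken on self-report (3.3).

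**Incentives.** Section 3 says that only ACTs bought after a test at the outlet "are eligible for the conditional subsidy", which exists in Arms 3 and 4. Outlets in Arms 2 and 4 are paid a small amount for performing RDTs.

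**Analysis.** Section 6.4 has no sensitivity analysis concerning outside tests.

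**The concern.** A client who had only a blood test at a laboratory may reasonably say that they have not sought treatment or care. That client never reaches 2.8, so a positive result on paper in their hand is not recorded, and no analysis can recover it later. If they buy an ACT without an outlet test, they enter the denominator but not the numerator, contrary to the protocol's own definition.

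With equal loss in every arm this would be a modest nuisance. The incentives make equal loss doubtful. In Arms 3 and 4 the client must repeat the test at the outlet to get the discount, and a repeat positive puts them in the numerator by another route. An Arm 1 client has no such reason. The same kind of client could then be counted as targeted in Arm 4 and untargeted in Arm 1, and this is the primary comparison.

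The secondary outcomes are exposed in a related way. Referred positives are meant to be left out of them, but a client whose outside result was never recorded cannot be identified and removed. For testing uptake, that client counts as tested if retested, and as untested if they bought an antimalarial without a retest.

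**Working it through.** **1. Tracing one client through the form.** Take a client with a documented laboratory positive who buys an ACT.

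| Answer at 2.5 | Tested at outlet | What the form records | Scored positive? |
|---|---|---|---|
| Yes | No | 2.8 to 2.10: positive, report seen | Yes |
| Yes | Yes, positive | 2.8 to 2.10 and 3.3 | Yes |
| No or don't know | Yes, positive | 3.3 only | Yes |
| No or don't know | No | at most 3.2 option 8, no result | **No** |

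Only the last row is an error, and it is an undercount. The rows scored positive are right under Section 6.1.

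**2. The plan's own figures.** 48 × 170 = 8160 interviews and 12 × 170 = 2040 per arm, as stated. The planned primary difference is 40 − 15 = 25 points. The 89% power for Arm 4 versus Arm 3 (40% v 26%) cannot be confirmed or refuted, because the share of interviewees who buy an ACT is not given. With ICC 0.006, two-sided alpha 0.05/3, 12 outlets per arm and a t-test on 22 df, 89% is reached at about 33 ACT buyers per outlet (33/170 = 19%):

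- design effect 1 + 32 × 0.006 = 1.192
- SE = √[(0.26 × 0.74 + 0.40 × 0.60) × 1.192/(12 × 33)] = 0.0361
- 0.14/0.0361 = 3.88, power 0.89

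I use 33 below as an inferred value.

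**3. Size of the artefact.** Let x be the share of ACT buyers with an outside positive that the outcome does not count unless they retest. Let r be the share of them who retest positive at the outlet. With x equal across arms and the same clients buying ACTs either way,

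bias (Arm a − Arm b) = x × (r_a − r_b).

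The documents give neither x nor r. For Arm 4 versus Arm 1 with r = 0 in Arm 1 (assumed):

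| x | r = 25% | r = 50% | r = 100% |
|---|---|---|---|
| 1% | 0.25 | 0.5 | 1.0 |
| 2% | 0.5 | 1.0 | 2.0 |
| 5% | 1.25 | 2.5 | 5.0 |

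Entries are percentage points. Some retesting in Arm 1 shrinks them: at x = 5%, r = 50% in Arm 4 and 10% in Arm 1 gives 5 × 0.4 = 2.0 rather than 2.5.

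**4. The other comparisons.** If the provider payment in Arm 2 produces as much retesting as in Arm 4, the Arm 4 versus Arm 2 bias is x × 0 = 0. At x = 5% with r = 60% in Arm 4 and 40% in Arm 2 it is 5 × 0.2 = 1.0 point. Arm 4 versus Arm 3 is 0 if both retest equally; 60% v 50% gives 5 × 0.1 = 0.5 point.

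**5. Effect on the test.** Suppose Arms 4 and 1 truly do not differ, with 15% in Arm 1 and 33 ACT buyers per outlet. The nominal upper-tail rejection rate is 0.05/3/2 = 0.83%.

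- 2-point artefact: SE 0.0284, 0.02/0.0284 = 0.70, rejection about 4%.
- 5-point artefact: SE 0.0294, 0.05/0.0294 = 1.70, rejection about 21%.

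If all 170 interviewees per outlet bought an ACT, these would be about 11% and 65%.

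**The case against.** **Few clients may take the faulty path.** The definition concerns people referred with a document, and most would say they had sought care. Item 2.6 lists "Visit private laboratory" among the answers after a yes, so the form itself treats a laboratory visit as care, and interviewers are trained. This stands as a reason to expect x to be small. It does not close the gap, because the client sees that list only after passing 2.5. Option 8 at 3.2 would expose some of the contradictions, but not the result.

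**Arms 3 and 4 are not the only arms with a push to retest.** This stands. Arm 2 outlets are paid to perform RDTs, so a clear upward bias in Arm 4 versus Arm 2 cannot be claimed.

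**Undocumented positives are left out by design.** This stands. Leaving out code 4 at 2.9 is the prespecified definition, not an error, and the form already collects what a sensitivity analysis would need. The difference in proof (self-report for outlet tests, paper for outside tests) is a reason to run that analysis, not to change the primary definition.

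**A retest may be real targeting.** A claimed, old or misremembered positive may turn negative at the outlet, and the client may then not buy an ACT. That is an effect the trial sets out to measure. Counting code 4 as positive in all arms could hide it, so that analysis can only be supportive.

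**A stronger reading.** A reader might infer that the figures for Arms 3 and 4 are themselves inflated, or that bias is demonstrated. The documents do not support either. A client who tests positive at the outlet and buys an ACT is counted correctly; the error is an undercount where retesting is rarer. Its size rests wholly on assumed values.

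**Conclusion.** The skip is a real defect in measuring the primary outcome: the form can score a client as not positive whom Section 6.1 counts as positive, and the lost result cannot be recovered. The discount rule gives a sound reason to expect the undercount to be larger in Arm 1 than in Arm 4, so the primary contrast may be inflated. No more than that can be said about size. The range of 0.25 to 5 points assumes x of 1 to 5%, r of 25 to 100% in Arm 4, no retesting in Arm 1, and equal x across arms. The part of x due to the skip is error; the part due to missing paper follows the protocol's definition.

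If the planned 25-point difference is real, an artefact in this range would not change the conclusion for Arm 4 versus Arm 1, though it would overstate the effect. It matters more if the true effect is small. The change is worth making because it is cheap and can only be made while data are being collected.

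**What to change.** 1. **Form.** Ask 2.8 to 2.10 of every client whatever the answer to 2.5, most simply by placing them before 2.5. The skip at 2.8 for clients with no test must then lead to 2.5 rather than 3.1.
2. **Form.** Route a client who ticks option 8 at 3.2 to 2.8 to 2.10 if these are unanswered, before Section 4.
3. **Section 6.1.** Keep the documented-only definition as primary.
4. **Section 6.4.** Prespecify one sensitivity analysis of the primary outcome that counts code 4 at 2.9 as positive in all arms. State that it is supportive, because a retest that turns negative may be an intervention effect.
5. **Reporting.** Give by arm the number of outside positives (documented and stated only), how many were retested at the outlet, and the outlet results. If interviews have already been done on the present form, also report by arm how many clients ticked option 8 at 3.2 with 2.8 unanswered. This counts only those who volunteered an outside test and does not recover the results.

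The cost is a skip change on the tablet, seconds per interview and one extra model run.

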### Section 3: Test at Shop

| Number | QUESTION   | RESPONSE   | SKIP                   |
|--------|--|--|------------------------|
| 3.1    | Did you (or your child) have your blood tested for malaria today at the shop? | 
1. Yes
 
2. No
   | If yes skip to 3.3     |
| 3.2    | Why not? (Mark all that apply)  | 
1. Too expensive
 
2. RDT was not offered
 
3. RDT not in stock
 
4. No time
 
5. Already sure illness is malaria
 
6. Already sure illness is not malaria
 
7. Don't want to get finger pricked
 
8. Was tested elsewhere before coming
 
9. Had a prescription for drug I needed before coming
 
99. Other
 | Next skip to section 4 |

|     |  |  |  |
|-----|--|--|--|
|     |  | Specify: _____                           |  |
| 3.3 | RDT results from shop (self-report) | 1. Negative
2. Positive
3. Invalid |  |
| 3.4 | How much did you pay for the RDT?   | _____ Naira                              |  |

